16.1.4 General Specifications for PK Concentration and PK Parameter Data

Predose samples that occur before the first drug administration will be assigned a time of 0 hours, as if the sample had been taken simultaneously with the study intervention administration. Same applies to the pre-dose sample after multiple doses.

Predose or trough samples which have been taken after the subsequent dosing will be reported as a protocol deviation. The resulting concentrations will be included in concentration listings but excluded from descriptive statistics of concentrations and from PK parameter estimation.

Values BLQ will be taken as zero for summary statistics of PK concentration data, PK parameter estimation (e.g. AUC) and for graphical presentations.

Missing concentrations (e.g. no sample, insufficient sample volume for analysis, no result or result not valid) will be reported and used generally as “N.R.”. A participant who withdraws prior to the last planned observation will be included in the analyses up to the time of discontinuation if still included in the PK analysis set.

If samples are collected outside of 10% of the PK sampling time windows defined in the CSP in section 8.4, these will be included in the PK parameter estimation (NCA) but will be excluded from the concentration summary and mean/median concentration plots.

PK concentrations which are erroneous due to a sampling processing or analytical error (as documented in the bioanalytical report) may be excluded from the PK analysis if agreed by the Sponsor. In this case the rationale for exclusion will be provided in the CSR. Any other PK concentrations that appear implausible to the Clinical Pharmacologist/Clinical PK/PD Scientist will not be excluded from the analysis. Any implausible data will be documented in the CSR.

If important protocol deviations occurred likely to affect the PK profile of participants as specified in Section 10.2.1, the impacted concentrations and PK parameters will be excluded from summary statistics and further statistical evaluation.

Any PK concentrations or PK parameters excluded from summary statistics will be included in participants listings and flagged; a reason for exclusion will be detailed in the CSR (e.g. a footnote or a table of exclusions). Any flags should be included in the study specific CDISC data sets.

PK concentrations and PK parameters excluded from summary statistics will not be included in mean/median figures. Mean plots will only contain values where $n > 2$.

In case of missing or incomplete urine samples, affected urine PK parameters might not be calculated.

16.1.5 Estimation of Pharmacokinetic Parameters

The computer program Phoenix® WinNonlin® version 6.4, or higher (Certara, L.P., [name],

Princeton, NJ 08540) will be used to derive PK parameters applying noncompartmental analysis (NCA).

The statistical software SAS® (Statistical Analysis System, SAS-Institute, Cary NC, USA, windows version 9.1 or higher) will be used to generate additional PK parameters and produce tables, listings, and figures.

16.1.5.1 Estimation of Pharmacokinetic Parameters in Plasma

PK parameters will be calculated using the actual elapsed time since dosing. In cases where the actual sampling time is missing, calculations may be performed using the scheduled time. Details (e.g. number of samples, participants affected) will be described in the CSR. In cases actual dosing time is missing, scheduled time might be used for NCA after performance of adequate plausibility checks and agreement with the sponsor. Decision and rational should be included in the CSR. Otherwise, there will be no further imputation of missing data.

The following plasma PK parameters will be calculated where appropriate for the transporter substrates digoxin, metformin, rosuvastatin, and sumatriptan:

Symbol	Definition
AUC _{0-∞}	The area under the concentration-time curve (AUC) from time zero (= dosing time) extrapolated to infinity, based on the predicted value for the concentration at t_{last} , as estimated using the linear regression from λ_z determination. $AUC_{0-\infty} = AUC_{0-t_{last}} + C_{last\ pred}/\lambda_z$
AUC _{0-t_{last}}	The AUC from time zero (= dosing time) to the last sampling time (t_{last}) at which the concentration is at or above the lower limit of quantification. Calculated using the mixed log-linear trapezoidal rule (linear up, log down).
AUC ₀₋₃₆	The AUC from time zero (= dosing time) to 36 hours postdose (metformin only). Calculated using the mixed log-linear trapezoidal rule (linear up, log down).
C _{max}	Maximum observed concentration.
t _{lag}	The time prior to the first concentration at or above LOQ.
t _{max}	The time to reach the maximum observed concentration collected during a dosing interval (the first occurrence in the case of multiple/identical C _{max} values).
t _{1/2}	Apparent terminal half-life. $t_{1/2} = \ln(2)/\lambda_z$
CL/F	The apparent total body clearance of study intervention following extravascular administration. $CL/F = Dose_{p.o.}/AUC_{0-\infty}$
V _z /F	The apparent volume of distribution during the terminal phase following extravascular administration. $V_z/F = Dose/(AUC_{0-\infty} * \lambda_z)$ following single dose.

$C_{last\ pred}$ = the predicted concentration at the last sampling time, calculated from the log-linear regression line for λ_z determination.

Additional PK parameters may be calculated where appropriate.

Units for PK parameter output will be based on concentration and dose units used in the study, unless otherwise specified. In case concentration data units change within the study, PK parameters

will be reported using consistent units throughout study outputs. In such cases, the Sponsor will specify relevant units for reporting before the final PK evaluation.

The parameters C_{max} and t_{max} will be obtained directly from the concentration-time profiles. If C_{max} occurs at more than one timepoint, t_{max} will be assigned to the first occurrence of C_{max} .

In cases where the actual observation time is not equal to the scheduled observation time, partial AUC_{0-36} until 36h will be calculated based on the estimated concentration at 36h and not the concentration at the actual observation time.

The following rules might be applied for calculation of partial AUC, after agreement with the Sponsor:

- In case suitable regression cannot be performed, partial areas may be calculated using the actual sampling time provided it is within 10% of the actual sampling time.
- In cases BLQ concentrations occur at the end of the collection interval, these concentrations might be set to missing for calculations of partial AUCs. This is an exemption to the general BLQ handling rule and should be applied in case its application would result in estimation of implausible partial AUC values. Implausibility is considered in cases partial AUCs were greater than $AUC_{0-\infty}$.

The following PK parameters will be calculated for diagnostic purposes and listed, but will not be summarized:

- First (λ_z low) and last (λ_z up) time point of the time interval of the log-linear regression to determine λ_z .
- Number of data points ($N\lambda$) included in the log-linear regression analysis to determine λ_z .
- Goodness of fit statistic (adjusted R^2) for calculation of λ_z .
- AUC from time t_{last} extrapolated to infinity given as percentage of $AUC_{0-\infty}$. ($AUC_{extra\%}$)
- Span ratio of interval over which $t_{1/2}$ was estimated/ $t_{1/2}$

The regression analysis should contain data from at least 3 different time points in the terminal phase consistent with the assessment of a straight line on the log-transformed scale. Phoenix WinNonlin “best fit” methodology will be used as standard. If warranted, further adjustment may be made by the pharmacokineticist, after agreement with the Sponsor. The last quantifiable concentration $> LLOQ$ should always be included in the regression analysis, while the concentration at t_{max} and any concentrations BLQ which occur after the last quantifiable data point $> LLOQ$ should not be used.

If $AUC_{extra\%} > 20\%$ and/or the coefficient of correlation (R^2 adj) of λ_z is < 0.8 and/or the observation period over which the regression line is estimated (span ratio) is less than 2-fold the resulting $t_{1/2}$, the rate constants and all derived parameters (e.g. $t_{1/2}$, $AUC_{0-\infty}$, CL/F , etc.) will be listed, flagged and included in the parameter outputs. Should more than 10% of subjects be flagged for AUC_{extra} and/or R^2 adj (for a particular analyte), a sensitivity analysis excluding flagged parameters may be performed after discussion with the Sponsor.

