Blood sampling times (transporter cocktail)	Predose, 0.33, 0.67, 1, 1.5, 2, 3, 4, 6, 8, 10, 12, 16 hours postdose	24, 36 hours postdose	48, 60 hours postdose	72 hours postdose	Predose 0.33, 0.67, 1, 1.5, 2, 3, 4, 6, 8, 10, 12, 16 hours postdose	24, 36 hours postdose	48, 60 hours postdose	72 hours postdose
Urine sampling intervals (metformin)	Predose, 0 to 4, 4 to 8, 8 to 12 hours postdose	12 to 24, 24 to 36 hours postdose			Predose, 0 to 4, 4 to 8, 8 to 12 hours postdose	12 to 24, 24 to 36 hours postdose		
Blood sampling times (evobrutinib)					1 hour ^a	1 hour ^a	1 hour ^a	

Note: for associated sampling time windows see Section 8.4 (Table 4).

a Post morning evobrutinib dose.

Part 2: Schedule of Assessments

Assessments & Procedures	Screening	Intervention Period (Days)									Safety Follow-up	Notes	
Study Day	-28 to -2	-1	1	2	3	4	5	6	7	8	9		
Informed consent	X											Prior to any Screening activity.	
Participants resident in the CRU		< ----- >											
Eligibility criteria	X	X										For re-check of eligibility criteria on Day -1, Sections 5.1 and 5.2.	
Demography, height & weight, medical history	X											Demography to include, at minimum, age, sex, race, and ethnicity.	
Physical examination	X	X									X	Brief examination on Day -1 to check eligibility.	
Serum pregnancy test	X	X									X		
Viral serology, TSH and QuantiFERON® test	X												
Clinical laboratory tests	X	X									X	X	Details in Appendix 5.
Cotinine, drug screen, alcohol breath test, SARS-CoV-2 and FSH	X	X											FSH in postmenopausal women at Screening only.
ECG & vital signs	X	X	X								X	X	Predose
CCI													
Sumatriptan administration			X								X		Single dose, fed conditions (Sections 5.3.1 and 6.1).
PK samples sumatriptan			X	X							X	X	Table 2 and Section 8.4.
Evobrutinib administration			X	X	X	X	X	X	X	X			Twice daily, fed conditions (Sections 5.3.1 and 6.1).
PK blood sample evobrutinib								X	X	X			Table 2 and Section 8.4.
AE/concomitant medication review	X	X	X	X	X	X	X	X	X	X		X	

AE=adverse events, CRU=clinical research unit, ECG=electrocardiogram, FSH=follicle stimulating hormone, PK=pharmacokinetics, SARS-CoV-2=severe acute respiratory syndrome coronavirus type 2, TSH=thyroid stimulating hormone.

Table 2 **Part 2: PK Sampling Schedule**

Sample type	Day 1	Day 2	Day 6	Day 7	Day 8	Day 9

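### Does keeping flagged AUC0-∞ values in the primary analysis, with only an optional sensitivity analysis, undermine the primary AUC ratio?

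*SAP*

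**What the plan says.** AUC0-∞ and Cmax are the primary endpoints (Protocol section 3; SAP section 5). For Part 1 the last cocktail blood sample is at "72 hours postdose" (Protocol Table 1).

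SAP 16.1.5.1 asks for a terminal regression on at least three time points and sets three limits:

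- extrapolated share above 20%;
- adjusted R² below 0.8;
- a regression interval where "the observation period over which the regression line is estimated (span ratio) is less than 2-fold the resulting" half-life.

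A parameter that misses any limit "will be listed, flagged and included in the parameter outputs". The follow-up rule begins "Should more than 10% of subjects be flagged for" extrapolation and/or R², counted per analyte, and ends with "a sensitivity analysis excluding flagged parameters may be performed after discussion with the Sponsor". Span is not named in that rule.

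Neither the PK Analysis Set (SAP 8.1) nor the primary model (SAP 16.1.3) removes flagged values. That they enter the primary model is an inference, though a safe one, since the optional analysis is the one that leaves them out.

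Protocol 9.4.3 and SAP 16.1.3 also commit, without condition, to analysing AUC0-tlast of every substrate with the same model as the primary endpoints. The span ratio, extrapolated share and adjusted R² are listed for each participant.

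**The concern.** The SAP sets limits on the quality of the terminal fit and then keeps the values that miss them. The only named check is optional, depends on a discussion with the sponsor in an open-label trial, and cannot be started by span failures. By contrast, the sensitivity analyses in SAP 16.1.3 are firm commitments.

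If one probe is eliminated slowly compared with 72 h of sampling, many of its AUC0-∞ values could be flagged. The primary AUC ratio for that probe, which may inform co-administration advice, would then rest largely on extrapolated tails. The confidence interval would be wider, and no analysis would be certain to show whether the ratio depends on those tails.

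**Working it through.** The plan states no figure for this point. It gives no half-life, quantification limit or expected extrapolated share, and the precision section is redacted. Half-lives below are therefore assumptions, shown as a range.

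**1. When the limits fail.** With a single terminal phase and a last sample at 72 h, the extrapolated share is 2^(−72/t½).

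- It exceeds 20% when t½ > 72·ln2/ln5 = 31.0 h.
- Span is (72 − start of regression)/t½. It falls below 2 when t½ exceeds 30, 24, 18 or 12 h for a regression starting at 12, 24, 36 or 48 h.
- More than 10% means at least 2 of 16 or 3 of 20 participants.

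Between roughly 12 and 31 h, then, a value can be flagged on span alone and not count towards the trigger. In simulation at 24 h, 31 to 51% of profiles did so.

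**2. What a span-only failure costs.** At t½ = 24 h the extrapolated share is 2^(−3) = 12.5%. Hold the predicted last concentration fixed and let the terminal slope be wrong by 20%:

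- slope too high: 12.5% × (1/1.2 − 1) = −2.1% of AUC0-∞;
- slope too low: 12.5% × (1/0.8 − 1) = +3.1%.

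The group that the trigger misses is the one in which the tail matters least. Where the tail is large (36 h and above), the simulated chance of at least 2 of 16 meeting the existing trigger was at least 98%, counting one profile each. At 30 h it ranged from 7 to 99% with the assumed error and profile shape, but the single-phase share there is 2^(−2.4) = 18.9%, still inside the SAP's limit.

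**3. Keep, exclude or truncate.** Simulation on the Table 1 times with a true AUC0-∞ ratio of 1.33:

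| Assumed t½ | Flagged values kept (as planned) | Flagged values excluded | Left of 16 |
|---|---|---|---|
| 18 h | 1.31–1.33 | 1.31 | about 7 |
| 24 h | 1.31–1.33 | 1.27 | about 3 |
| 30 h | 1.31–1.33 | 1.16 | about 0 |
| 36 h or more | 1.31–1.33 | not usable | almost none |

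The range in the second column covers all half-lives tried. AUC truncated at 72 h gave 1.27, falling to 1.14 over the same half-lives. A repeat run with 10% residual error and within-subject CVs of 10% on clearance and 12% on bioavailability showed the same pattern.

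A separate simulation gives similar attrition. The shares flagged on either day at 24/30/36/40/48 h (extrapolation or R², plus span only) are 6+56, 29+53, 60+36, 73+26 and 90+10, that is 62/82/96/99/100%. Of 16 participants that leaves about 6/3/1/0/0. SAP 16.1.2 does not compute even descriptive statistics unless n exceeds 2.

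**4. Why exclusion and truncation pull towards 1.** Flagging depends on half-life, and inhibition of clearance lengthens half-life, so exclusion removes the participants most affected. For truncation, let clearance fall by 25% with volume unchanged, so that t½ goes from 36 to 48 h. The AUC0-∞ ratio is 1/0.75 = 1.33. The AUC0-72 ratio is 1.33 × (1 − 2^(−1.5))/(1 − 2^(−2)) = 1.33 × 0.646/0.750 = 1.15.

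**5. Whether a check is assured.** If 72 h is quantifiable on both days, tlast is 72 h on both, and AUC0-tlast is AUC0-72. That is the situation expected for a slowly declining probe, and the analysis is already mandatory.

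**The case for a change.** The strongest case is textual, and its reading is right. The check is optional, span cannot start it, and the SAP does not say outright that flagged values enter the primary model. Firm wording would cost almost nothing. Span failures are not ignored, however: they are computed, listed and flagged, and an analysis that leaves out flagged parameters could drop them too once it is run.

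A second argument is that AUC0-tlast is an imperfect companion. Its endpoint can differ between Day 1 and the evobrutinib day, and step 4 shows that it understates an interaction that prolongs half-life. Both points are true. They argue for reading it beside AUC0-∞, not for letting a truncated measure replace the protocol's primary endpoint. If 72 h is not quantifiable, AUC0-72 is not fully observed either.

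Third, extrapolation costs precision. In simulation, the SD of the within-subject log ratio for AUC0-∞ was 1.10 to 1.37 times that for AUC0-72, so intervals are about 10 to 37% wider. That follows from the choice of endpoint and the sampling horizon, and the reported 90% CI shows it. It is not bias, and the study tests no hypotheses (Protocol 9.1).

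**Conclusion.** The concern does not hold. Followed as written, the plan gives an essentially unbiased primary AUC0-∞ ratio (1.31 to 1.33 for a true 1.33 across assumed half-lives of 18 to 48 h) and an unconditional extrapolation-free analysis beside it. Making exclusion of flagged values the decisive check would leave few or no participants and bias the ratio towards no interaction.

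That sampling to 72 h makes failures likely for digoxin cannot be shown from the documents. It is conditional on a half-life above about 31 h for extrapolation, or above 12 to 30 h for span, depending on where the regression starts.

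What remains is that the check is optional and its trigger omits span. This is missing detail that leaves the primary result sound. The conclusion assumes a half-life effect through clearance, concentrations quantifiable to 72 h, and the simulated error and profile shapes. The half-life thresholds do not depend on the assumed error.

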4.2 Scientific Rationale for Study Design

The study design and endpoints are typical for a DDI study of this type. The effect of evobrutinib on transporter activities will be investigated by measurement of the PK of the transporter substrates digoxin, metformin, rosuvastatin, and sumatriptan. Oral administration of the probe drug transporter substrates is expected to be a sensitive test for potential interactions with drug transporters such as P-gp, MATE1/MATE2-K, BCRP, and OCT1 since they reflect effects on both presystemic and systemic clearance. The transporter substrate cocktail (digoxin, metformin, and rosuvastatin) will be administered during Part 1 of the study as a reference treatment on Day 1 followed on Day 4 through Day 12 by multiple doses of evobrutinib twice daily, with a second dose of substrate cocktail given with the morning dose of evobrutinib on Day 10. During

Part 2, sumatriptan will be administered on Day 1 as reference and on Day 8, and evobrutinib will be administered twice daily on Days 2 through 8.

A single-sequence design for Part 1 and Part 2 was chosen because the exact mechanism of inhibition of the transporters by evobrutinib and therefore the time course of on- / offset of these effects are not known. Therefore, evobrutinib will be administered twice daily for 6 days before the second administration of transporter substrates in each study part.

The transporter substrate cocktail to be used in Part 1 of this study (digoxin [0.25 mg], metformin [10 mg] and rosuvastatin [10 mg]) has been optimized as a screening tool for transporter mediated DDIs (Wiebe 2020, Stopfer 2018) based on PK analyses of the substrates both separately and in combination. The safety profiles of the individual substrates of the cocktail are well established since these drugs are routinely used in clinical practice. Stopfer reported mild or moderate adverse events in 15 of 30 participants (Stopfer 2018). Similarly, for Part 2, sumatriptan (25 mg) has been recommended and used as a substrate for determining PK effects of potential OCT1 effectors (Chu 2018). The safety profile of sumatriptan is well established since it is routinely used in clinical practice (Sumatriptan SmPC).

Because some of the transporters to be investigated in this study might exist as polymorphic variants, which could affect the interpretation of the study results, samples for CCI [REDACTED] will be collected and analyzed.

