8.1 Definition of Analysis Sets

Analysis Set	Description
Screening	All participants, who provided informed consent, regardless of the participant's enrollment and study intervention status in the study.
Safety (SAF)	All participants, who were administered any dose of any study intervention. Analyses will consider participants as treated.
Pharmacokinetic (PK)	
The PK Analysis Set is a subset of the SAF, and the PK population will include all participants:
 
• Who have completed the study without any relevant protocol deviations and factors likely to affect the comparability of PK results.• With adequate study intervention compliance. 
With evaluable PK data, i.e., no missing values for primary endpoints at each PK profile/assessment day (Day 1, Day 10 for Part 1; Day 1 and Day 8 for Part 2).
 
If participants received prohibited concomitant therapy or medicines, as specified in Section 6.8.3 of the protocol, they will be excluded from the PK population.
 
All PK analyses will be based on this analysis set.

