16.1.3 Statistical Analysis of PK Parameter Data

Part 1

- **Analysis of Primary Endpoints**

A general linear model with a fixed effect for TREATMENT and a random effect for SUBJECT will be applied to log-transformed PK parameters C_{max} and $AUC_{0-\infty}$ based on the PK analysis set to assess the effect of multiple doses of evobrutinib on the PK of the transporter substrates digoxin, metformin, and rosuvastatin. Treatment differences on the log scale of transporter substrates with evobrutinib vs substrates alone (Day 10 versus Day 1) will be estimated for C_{max} and $AUC_{0-\infty}$ together with their 90% CIs.

Point estimates and CIs will be back transformed to the original scale.

- **Analysis of Secondary Endpoints**

[figure not shown]
The same analysis model as described for the primary endpoints will be provided for the secondary endpoint $AUC_{0-t_{last}}$ of transporter substrates.

The same analysis model as described for the primary endpoints will be provided for the secondary endpoint CL_R of metformin only.

Sensitivity Analyses

The same analyses on the primary and secondary endpoints will be repeated including participants
CCI

Part 2

- **Analysis of Primary Endpoints**

A general linear model with a fixed effect for TREATMENT and a random effect for SUBJECT will be applied to log-transformed PK parameters C_{max} and $AUC_{0-\infty}$ based on the PK analysis set to assess the effect of multiple doses of evobrutinib on the PK of the transporter substrate sumatriptan. Treatment differences on the log scale of sumatriptan with evobrutinib vs sumatriptan alone (Day 8 versus Day 1) will be estimated for C_{max} and $AUC_{0-\infty}$ together with their 90% CIs.

Point estimates and CIs will be back transformed to the original scale.

- **Analysis of Secondary Endpoints**

The same analysis model as described for the primary endpoints will be provided for the secondary endpoint $AUC_{0-t_{last}}$ of sumatriptan.

Sensitivity Analyses

The same analyses on the primary and secondary endpoints will be repeated including participants
CCI

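### Does the loosely worded exclusion of flagged AUC0-inf values in SAP 16.1.5.1 need tightening?

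*SAP*

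**What the plan says.** SAP 16.1.5.1 sets three quality criteria for the terminal slope: extrapolated AUC above 20% of the total, adjusted R² below 0.8, or "the observation period over which the regression line is estimated (span ratio) is less than 2-fold the resulting" half-life. A result that fails any of them "will be listed, flagged and included in the parameter outputs", so it remains in the primary analysis.

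The next sentence sets the trigger. It begins "Should more than 10% of subjects be flagged for" and then names extrapolated AUC and adjusted R², per analyte, but not span. If the trigger is met, "a sensitivity analysis excluding flagged parameters may be performed after discussion with the Sponsor".

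Four other places bear on this:

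- The slope diagnostics "will be calculated for diagnostic purposes and listed, but will not be summarized" (SAP 16.1.5.1).
- The PK Analysis Set requires "no missing values for primary endpoints at each PK profile/assessment day" (SAP 8.1).
- For AUC0-tlast, "The same analysis model as described for the primary endpoints will be provided for the secondary endpoint" (SAP 16.1.3), so it is modelled whether or not flags occur.
- Protocol 9.1 describes the analysis as descriptive, with no hypothesis tests.

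**The concern.** Three criteria create flags, two of them open the sensitivity analysis, and the exclusion then refers to flagged results without saying which. A span-only flag could be in or out. Nor does the sentence say whether one day's value or both are removed. The mixed model in SAP 16.1.3, with a random participant effect, would accept an unpaired value. Two programmers could therefore produce different ratios from the same data.

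There is also a possible direction. Protocol 4.2 calls oral probes sensitive "since they reflect effects on both presystemic and systemic clearance". If evobrutinib lowers systemic clearance, half-life lengthens on the evobrutinib day, the extrapolated share rises and flags gather there. Removing them takes out high values of AUC0-inf and pulls the ratio towards 1. AUC0-tlast also under-reads a clearance effect, because it cuts off more of the curve on that day. Two secondary readings would then fall below a correct primary estimate for related reasons, and a reader might take their agreement as evidence against a real interaction.

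**Working it through.** The documents give no substrate half-life or LLOQ, and the variability and precision tables are redacted. There is no stated figure to reproduce, and the sizes below are illustrative.

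**Trigger.** About 16 evaluable participants per part, at most 20 assigned (Protocol 1.1). 10% of 16 is 1.6, so 2 flagged participants suffice; 10% of 20 is 2, so 3 are needed.

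**When 20% extrapolation is reached.** With one exponential, the tail beyond the last sample T is 0.5^(T/t½). Setting this to 0.20 gives t½ = T × ln 2 / ln 5.
- Part 1, T = 72 h: 31.0 h.
- Part 2, T = 24 h: 10.3 h.

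Example: a 24 h half-life on Day 1 leaves 0.5^(72/24) = 12.5%. With clearance × 0.70 it becomes 24/0.70 = 34.3 h and leaves 0.5^(72/34.3) = 23.3%. A typical participant is then unflagged on Day 1 and flagged on Day 10.

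**Simulation, clearance × 0.70, true ratio 1/0.70 = 1.43.** Protocol Table 1 sampling times. Assumptions: one compartment, absorption rate 1/h, between-participant CV 25% (clearance) and 20% (volume), within-participant CV 10% on clearance and on bioavailability, interaction spread 15%, assay error 8%, no LLOQ limit. Exclusion uses the two trigger flags unless stated.

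| Assumed Day 1 half-life | 20 h | 24 h | 30 h |
|---|---|---|---|
| Flagged, Day 1 / Day 10 | 11% / 42% | 23% / 59% | 46% / 79% |
| All values kept (primary) | 1.43 | 1.43 | 1.42 |
| Pairs removed | 1.35 | 1.32 | 1.27 |
| Single values removed | 1.31 | 1.27 | 1.23 |
| AUC0-tlast | 1.27 | 1.25 | 1.21 |
| Median pairs left of 16, two flags | 9 | 6 | 3 |
| Median pairs left of 16, three flags | 5 | 3 | 1 |

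A closed-form check of AUC0-tlast at 24 h: 1.43 × (1 − 0.233)/(1 − 0.125) = 1.25, as simulated.

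**How much the two open choices matter.**
- *Span.* In a second simulation (true ratio 1.50, 24 h half-life, within-participant CV about 15%), two flags against three gave 1.39 and 1.38 with pairs removed, and 1.33 both ways with single values removed. Span costs precision rather than changing the estimate.
- *Unit.* Pair against value in the table: 1.35 − 1.31 = 0.04, 1.32 − 1.27 = 0.05, 1.27 − 1.23 = 0.04. On the log scale, ln(1.35/1.31) = 0.030, ln(1.32/1.27) = 0.039 and ln(1.27/1.23) = 0.032. The trial-to-trial SD of such an estimate is 0.08 to 0.16, so the gain is less than half of it.

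**Precision if the step is run.** The 90% CI half-width factor is exp(t0.95,n−1 × 0.26/√n), where 0.26 is the simulated SD of the log ratio. This gives 1.12 for 16 pairs, 1.24 for 6 and 1.55 for 3. A badly depleted analysis shows itself in its interval.

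**Where the pull is absent or reversed.**
- Presystemic effect at 24 to 36 h: 1.42 to 1.46 against 1.43.
- No effect: 0.99 to 1.01.
- No within-participant variation in clearance and a uniform effect: pair removal gives 1.42 at 20, 24 and 30 h; value removal 1.38 to 1.40.
- Half-life 10 h with an LLOQ at 20% of Cmax: 1.48 (pair) and 1.53 (value), above the true 1.43.
- No LLOQ limit: the trigger is met in 4 to 6% of trials at 10 h with 72 h sampling, and in none at 2 h with 24 h sampling.

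**The case for a change.** The case for amending the text is respectable. The gap is plain on the page. It could be closed before database lock with a few sentences and a small count table. Settling the flags and the unit in discussion with the Sponsor, in an open-label study, means settling them with the data in view. A sensitivity analysis is there to test the primary result, and one that leans towards no interaction in a case the trial is designed to detect serves that purpose poorly.

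Part of this stands. Whether span-only flags exclude is unclear, and the under-reading under slowed elimination of a long-half-life substrate held up under different assumed inputs.

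The rest is weaker:

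- *Unit.* The sentence speaks of parameters, not participants. SAP 10.2.1 and 16.1.4 likewise exclude at the level of individual values and affected parameters. The literal reading is value by value, and the pairing condition in SAP 8.1 governs membership of the set. A pair rule would therefore be a change of method more than a missing definition.
- *Visibility.* Flags are listed by participant, analyte and day (SAP 16.1.5.1 and 16.1.6.1) for at most 20 people per part. Half-life, AUC0-tlast and AUC0-inf are summarized by day (SAP 16.1.2 and 16.1.6.1), so a longer half-life or a larger extrapolated share under evobrutinib would show. Applying the 10% trigger already requires a count of flagged participants per analyte.
- *Different programmers.* One organisation does the PK evaluation (SAP 16.1), and the discussion with the Sponsor comes first.
- *Misreading.* How AUC0-tlast and a depleted AUC0-inf analysis should be read against the primary result is a matter for the study report.

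**Conclusion.** No change is needed. The wording leaves a detail open in an analysis that may never be run. Flagged values stay in the primary analysis, which recovered the true ratio to within 0.01 in the tabulated scenarios. The study has no hypothesis test, and no stated decision rule rests on this step.

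The size of the problem is conditional. With clearance cut by 30% and half-lives of 20 to 30 h, the optional result would read 1.23 to 1.35 instead of 1.43. A pair rule would recover only 0.04 to 0.05 of that, and settling the span question would barely move the estimate. Those half-lives, the variability and the absence of an LLOQ limit are all assumed. The pull does not arise for a presystemic effect, nearly disappears under pair removal when clearance is stable and the effect uniform, and can reverse when the LLOQ truncates profiles.

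A sensible analyst who runs this step will state which flags were used and how many participants remain, and will read the result beside the by-day half-life summary. The trial's conclusion is sound with the plan followed as written.
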